3.6.1 Advantage of high field MRS

Figure 3 shows the ^{31}P spectra acquired using the 7T at the Center for Magnetic Resonance Research of the University of Minnesota by [name] and his collaborators⁴⁵. Collecting ^{31}P -MRS data at 7T offers more than twice as much signal to noise ratio (SNR) per unit time thus reducing measurement time compared to 3T magnet⁴⁶. In addition, the increase in SNR allows the measurement of MRS parameters in muscles of interest and with high temporal resolution (1 s). This is important because the Sol, as a postural muscle, is predominantly a slow twitch muscle (slow fatigue, primary source of ATP is oxidative phosphorylation) and the gastrocnemius muscles, are more active during locomotion, is a 50% fast twitch muscle (fast fatigue and primary source of ATP is anaerobic glycolysis). The effects of PAD on each muscle may be different and the benefits from treatment will depend on the metabolic characteristics of each muscle. Therefore, measuring oxidative phosphorylation in each muscle separately will provide us with a more accurate assessment of the effects of Entresto on the bioenergetics of skeletal muscles in patients with PAD.

3.6.2 MRS Exercise protocol

Individuals will perform a 24 s maximal isometric voluntary plantar flexion, while inside the magnet, to lower PCr resting levels by 50%⁴⁷. MRS will be performed for 1-min before the contraction, during the 16 s isometric contraction and throughout a 3 min recovery period. Maximal voluntary contraction will be measured in each individual while in the magnet using an MRI compatible device that is composed of a foot holder attached to a force transducer⁴⁸.

3.6.3 Rationale for measuring oxidative phosphorylation using MRS

Phosphocreatine resynthesis rates have been used as a surrogate measure of mitochondrial function⁴⁹ and has been studied non-invasively using MRS⁵⁰. MRS measured PCr resynthesis rate is independent of arterial occlusion⁵¹ and has been used to study the effects of exercise training and age on mitochondrial function^{47,52}. Furthermore, the rate of PCr resynthesis in patients with PAD is 2/3 lower than age matched non-PAD individuals, partially explaining their limitations with mobility^{51,53,54}. Therefore, measuring PCr resynthesis non-invasively is especially advantageous in patients with PAD in whom performing serial biopsies can cause wound healing complications. We expect that in patients receiving Entresto the rate of resynthesis of PCr will be increased and it will be associated with improvements in mobility.

3.7 Measurement of tissue perfusion and oxygenation using functional MRI (fMRI)

Validations studies using near infrared spectroscopy showed that changes in tissue oxygenation and blood volume can be assessed using differences in the MR signal intensities acquired using a dual echo gradient recall echo-echo planar (GRE-EPI) MRI procedure^{55,56}. This technique found differences in microvascular function between type 2 diabetic patients and healthy individuals⁴⁸.

3.8 fMRI data acquisition

[figure not shown]

Figure 4. GRE-EPI signal intensity time course before (blue), during (red) and following 16 seconds of maximal voluntary contraction (green) at a 7T magnet. a = post-contraction baseline, b = post-contraction peak. Change SI = b – a.

fMRI and MRS data will be acquired on the same magnet during a procedure that lasts about 90 minutes. MR signal intensities (SI) will be acquired using a custom made 6 cm diameter surface proton/phosphorus coil. The same anatomical site used for the MRS data will be used to acquire the fMRI. Muscle functional MRI (fMRI) data will be acquired using a GRE, echo-planar imaging sequence for 30 s before, during a 3 min cuff-occlusion, and for the following 210 s. The same procedure will be performed again after a 5 minute rest period using a spin echo (SE) sequence with similar acquisition parameters except with a TE = 21

ms. The functional images will be acquired using an acquired matrix = 128×128 , slice thickness = 10 mm, repetition time = 1000 ms (defining the time resolution of the measurements), and TE = 15 ms. In addition, MRS data will be acquired using a global signal using a free induction decay and adjusting the parameters to acquired preferentially from the MG muscle using a TR = 6 s Ernst angle = 77° and a T1 of PCr in muscle for $7T = 4$ s.

A couple of blood pressure measurement will be taken following a 5 minute rest and before entering the MRI scanner. The highest blood pressure value will be used to determine the level of cuff inflation during the cuff occlusion procedure. The cuff will be inflated using a Hokanson rapid cuff inflation system, which inflates the cuff around the thigh in a couple of seconds. The cuff will be inflated 75 mmHg above the systolic blood pressure or to a max of 275 mmHg. Before initiating the scanning session, blood pressure cuff will be inflated for about 10 seconds to the target pressure to show participants what they will feel and if they are ok with that level of pressure. Cuff pressure can be lowered by 10 mmHg for patient comfort, if necessary. Images will be acquired from the leg with the more severe claudication symptoms independent of the ABI values. If the patient has a stent or a bypass graft in one leg, images will be acquired from the contralateral leg. If there are stents or bypass graft in both legs then the patient may be excluded from the study. This will be discussed on an individual basis with the Co-PI [name] and the study physician [name].

3.8.1 Functional MRI data analysis

Images will be analyzed using custom-written Matlab version 7.0.1 (The Mathworks, Natick, MA) routines. The functional images will be co-registered to the anatomical image using a rigid registration procedure⁵⁷. Then the anatomical image will be used to identify the MG and Sol muscles and regions of interest (ROIs) will be specified separately around those two muscles. Resolved connective tissues and blood vessels will be excluded from the ROIs. The mean functional image SI for the ROI will be

calculated as a function of time and divided by the corresponding mean pre contraction SI value. An average SI time course will be obtained by averaging the SI time course from two trials, as previously described⁵⁶.

The averaged SI time course will be fitted to a polynomial function, and inflections in the derivative of this polynomial will be used to identify the minimum and maximum post contraction SI values. Figure 4 shows post contraction signal intensity indicating change in oxygenation plotted as a function of time. Data obtained at University of Minnesota CMRR 7T, unpublished observation. The change in SI ($\Delta SI = b - a$) will be determined for the Sol and MG muscle reflecting the average post contraction changes in oxygenation at the muscles microvascular bed.

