1.2 Study Aims/Objectives

Primary Objective:

1. To assess the effects of 12 weeks of Entresto on the functional clinical parameters maximal walking duration, pain free walking duration and 6 minute walk test of patients with PAD.

Secondary Objective:

1. To assess if changes in functional clinical parameters are related to improvements in microvascular and mitochondrial function and to assess the effects of increasing NP activity on arterial elasticity.
2. To assess the time required for functional improvements (6 minute walk test) to return to baseline

values following 12 weeks of Entresto.

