9.2 Power analysis

Sample size for a double blind randomized clinical trial was determined using SAS version 9.3 (SAS Institute Inc., Cary, NC, USA). Sample size is based on the mean (SD) values obtain in a clinical trial that measured the effects of carperitide on pain free walking distance in patients with PAD 5. The mean (SD) pre post change in pain free walking distance was of 278 (240) m. [We have estimated that for a power 0.85 we will need 15 subjects per group to reject the null hypothesis with Type I error probability of 0.05] (Figure 6).

10 Clinical Management

[name] Assistant Professor in the Department of Medicine Division of Kidney Diseases and Hypertension will be the study physician for clinical trial. This includes adjusting the dose of Entresto (based on information obtain from the Entresto information sheet, Novartis), development of safety procedures and treatment of medical complications. The main PI ([name] MD PhD) will be the person directly in charge of admittance of patients into the study, performing and supervising the diagnostic tests and the metabolic, physiological and clinical functional testing.

11 Risks/Benefits

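### Section 3.8.1's rule for finding the fMRI minimum and maximum does not locate extrema as worded, and the likely intended rule (first-derivative zeros) can still miss the minimum after cuff release

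*Combined protocol and SAP*

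**What the plan says.** Section 3.8.1 gives the derivation in two steps. First, "The averaged SI time course will be fitted to a polynomial function". Then "inflections in the derivative of this polynomial will be used to identify the minimum and maximum post contraction SI values". The difference ΔSI = b − a "will be determined for the Sol and MG muscle reflecting the average post contraction changes in oxygenation" in the microvascular bed. The Figure 4 legend, under section 3.8, gives the two values as "a = post-contraction baseline, b = post-contraction peak".

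Section 3.8 describes the acquisition: one image per second, through a 3 min cuff occlusion and for 210 s afterwards. Neither section states the polynomial degree or the fitting window.

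The measure serves secondary objective 1 in section 1.2: "To assess if changes in functional clinical parameters are related to improvements in microvascular and mitochondrial function". Section 9.1 plans regressions that link physiological change to walking function.

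**The concern.** A minimum or maximum of a smooth curve lies where its first derivative changes sign, or at an end of the window. An inflection of the derivative is where the third derivative is zero. Read loosely, as an inflection of the curve, it is where the second derivative is zero. Neither condition marks a low point or a peak.

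Correcting the word is not enough. If the signal rises as soon as the cuff is released, the low point is the first image. The slope is not zero there, so a search for derivative zeros passes over it.

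At stake is the plan's fMRI measure of microvascular function in each muscle. If a is missing, or is taken from the wrong part of the curve, ΔSI partly reflects polynomial degree and window rather than oxygenation. With about 15 patients per group, avoidable measurement error is costly to the mechanism analyses.

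**Working it through.** **Inputs.** From the documents: the rule and ΔSI = b − a (3.8.1), the meanings of a and b (Figure 4 legend), 1 s sampling and 210 s after occlusion (3.8). Assumed: all curve shapes, amplitudes, time constants, degrees and the shorter windows. All curves are noise-free. The plan states no value of ΔSI to reproduce.

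**1. Exact cubic.** Let f(t) = 1 + 0.03(3u² − 2u³), with u = t/10.

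- f′ = 0.018·u(1 − u): zero at 0 s and 10 s, with values 1.000 and 1.030. ΔSI = 0.030, the correct answer.
- f″ = 0.0018(1 − 2u): zero only at 5 s, with value 1 + 0.03(0.75 − 0.25) = 1.015. One point gives no difference.
- f‴ = −0.00036: never zero. The literal rule finds nothing.

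**2. Dip-then-peak curves, 30 s window.** SI(t) = 1 − d·exp(−(t − 3)²/8) + A·[(t/p)·exp(1 − t/p)]², with (A, p, d) = (0.03, 12, 0.02), (0.06, 15, 0.02) and (0.03, 20, 0.03). Each entry is the largest minus the smallest fitted value at the points found.

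| Degree | f′ = 0 | f″ = 0 | f‴ = 0 |
|---|---|---|---|
| 5 | 0.0440, 0.0736, 0.0518 | 0.0186, 0.0367, 0.0302 | 0.0123, 0.0072, 0.0034 |
| 6 | 0.0454, 0.0733, 0.0556 | 0.0239, 0.0266, 0.0358 | 0.0087, 0.0089, 0.0135 |
| 7 | 0.0457, 0.0740, 0.0564 | 0.0245, 0.0324, 0.0365 | 0.0130, 0.0049, 0.0174 |
| 9 | 0.0440, 0.0719, 0.0565 | 0.0355, 0.0370, 0.0423 | 0.0419, 0.0715, 0.0558 |

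At degrees 5 to 7, dividing each entry by the f′ value for the same fit, the f″ points give 36% (0.0266/0.0733) to 65% (0.0365/0.0564). The f‴ points give 7% (0.0034/0.0518) to 31% (0.0174/0.0564). At degree 9 the f‴ loss almost vanishes, so its size depends on a degree that the plan does not state.

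**3. First-derivative zeros after release.** Take SI(t) = 1 + A(1 − e^(−t/3))·e^(−t/30), a 3 s rise and a 30 s decay. At release f′(0) = A/3 > 0, so the low point before the peak is t = 0, where the derivative is not zero. Setting f′ = 0 gives e^(−t/3)·(1/3 + 1/30) = 1/30, so e^(−t/3) = 1/11 and t = 3·ln 11 ≈ 7.2 s. That is the only zero: b is found and a is not. The true b − a is A·(10/11)·e^(−7.2/30) ≈ 0.715A.

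Polynomial fits to assumed release curves over 210 s behave the same way.

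- In one set of 12 fits (three curves; degrees 5, 6, 7 and 9), no first-derivative zero came before the peak.
- In one set (degree 5 to 9), the rule gave 21% to 46% of the true b − a, or found fewer than two points.
- In another set it gave 63% to 101% where two zeros existed, but only by using a low point after the peak as a.

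An interior dip does not guarantee a valid a either. Fitting the step 2 curves over 60 s, the earliest zeros were at 14.0, 16.6 and 21.4 s (degree 5) and at 14.5, 16.3 and 19.5 s (degree 6). These are the peaks; the dip near 3 s is lost in all six fits.

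**4. Fitted-curve range, window ends included, a before b.** Over 210 s and degrees 5 to 9 this gave 85% to 100% of the true value for medium and slow release curves, and 31% to 87% for a fast one. A separate check on a 3 s rise with a 30 s decay gave 16% to 78%. On fast curves the degree therefore matters as much as the rule.

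**The case against.** The strongest reply is that this is a slip of terminology. The sentence names the minimum and maximum as its target, and the legend calls b a peak. A point on the slope is neither, so a reader would infer sign changes of the first derivative. The Matlab routines are custom-written, and nothing shows that they search for second- or third-derivative zeros. Figure 4 itself is not available here. All the percentages come from invented curves, and nothing in the documents says that the signal rises at the moment of release.

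Most of this stands. The slip is the likely explanation, and the sizes are not estimates for this trial. But the charitable reading leaves two things open: what happens when the minimum is at the window start, and whether a must come before b. The legend does not settle them, since it calls a a baseline where 3.8.1 calls it a minimum. Because the code is custom, this sentence is the only public specification of ΔSI.

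Three stronger inferences are tempting and should not be drawn.

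- That ΔSI will be wrong in the trial. The implementation is unknown.
- That the rule can reverse the sign of ΔSI. The plan seeks a minimum and a maximum, and maximum minus minimum cannot be negative. A reversal needs a selection rule that the plan does not contain.
- That the error is tied to treatment because the drug is expected to change fMRI recovery speed. The plan's stated expectation about a rate concerns phosphocreatine resynthesis by spectroscopy (3.6.3); ΔSI is an amplitude.

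**Conclusion.** The rule is wrong as worded, and its likely intended form is incomplete. The calculus needs no assumption: inflections are not extrema, and a minimum at the start of a rising curve is not a derivative zero. Whether such a minimum occurs depends on the signal rising at release, which the cuff-occlusion acquisition makes possible but the documents do not show.

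The size is uncertain. First-derivative zeros returned 21% to 46% of the true b − a, or nothing, on one set of assumed release curves, and 63% to 101% on another by using the wrong low point. The consistent finding across the release-curve fits is that no valid a was found before the peak. The point concerns a secondary, mechanistic measure. The primary walking outcomes and the sample size in section 9.2 do not depend on it.

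**What to change.** Replace the sentence in 3.8.1 with: b is the maximum of the fitted curve in the post-stimulus window, and a is the minimum of the fitted curve between the start of that window and b, with window ends included.

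State one polynomial degree and one window for all scans, fixed in advance and chosen so that the fit follows a fast early rise. Baseline scans, read blind to arm, could be used for this choice. It matters: low degrees lost about 70% of ΔSI on one fast assumed curve (100% − 31% = 69%), and 84% (100% − 16%) on another, even with the replacement rule.

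Reconcile the post-contraction wording in 3.8.1 and Figure 4 with the cuff-occlusion acquisition in 3.8, so that the start of the window is defined, and use one description of a in both places.

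The cost is a few lines of text and a few lines in the Matlab routine. No new data are needed.

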3.8.2 Rationale for functional MRI measurements

A 12 week supervised exercise training program for patients with PAD showed that increases in peak VO_2 was correlated with increases in capillary density and to a 70% improvement in peak leg blood flow measured using cuff occlusion plethysmography⁵⁸. These results show that the improvements in functional clinical parameters are related to an enhanced tissue perfusion of the leg. The fMRI technique allows for the measurement of post contraction changes in tissue oxygenation with a high temporal and spatial resolution. The assessment of microvascular function in the MG and Sol muscle separately will allow us to determine if the effect of Entresto may be muscle fiber type dependent. Theoretical calculations indicate that at 7T, SE acquired images reflect tissue oxygenation surrounding small vessels, whereas images acquired using GRE are reflective of oxygenation status in tissues surrounding small and large vessels.

4 Subjects

4.1 Study Setting

This study will take place at the University of Minnesota.

4.2 Eligibility Criteria

Inclusion Criteria

Subjects will be eligible to participate in the study if all of the following conditions exist:

1. Age 18-80 years of age
2. Intermittent claudication, such as exercise-induced pain, cramps, fatigue, or other equivalent discomfort, involving large muscle groups of the leg(s) (calf, thigh, buttocks), relieved by rest.
3. Ankle-brachial index ≤ 0.90 acquired according to the American Heart Association guidelines.
4. Highest ankle pressure reduced by at least 25 mm Hg after exercise compared to resting pressure (or loss of previously present Doppler signal for both the posterior tibial and anterior tibial arteries immediately after exercise if arteries were incompressible).
5. Patients on medical treatment for PAD without significant improvement in intermittent claudication within the last 6 months.
6. Absence of more than 60% renal artery stenosis within the last year. If a duplex ultrasound has not been performed within the last year to detect renal artery

stenosis, it will be schedule during the screening visit.

7. For women with reproductive potential, a willingness to use methods of contraception that will prevent the subject from becoming pregnant during the study. Adequate contraception methods include hormonal methods used for two or more menstrual cycles before Screening (eg, oral contraceptive pills, contraceptive patch, or contraceptive vaginal ring), barrier methods (eg, contraceptive sponge, diaphragm in conjunction with contraceptive foam or jelly, or condom in conjunction with contraceptive foam or jelly), intrauterine methods (IUD), sterilization (eg, tubal ligation or a monogamous relationship with a vasectomized partner) and abstinence.

Exclusion Criteria

Subjects will be excluded from participation in the study if any of the following conditions exist:

1. Patients with physician diagnosed heart (HF) stage > II, liver failure or cancer other than skin cancer.
2. Estimated glomerular filtration rate (eGFR) < 30 mL/min/1.73 m².
3. Severe limitations in mobility due to osteomuscular disorders.
4. Dementia or other mental disorders that prevent patients from following a research protocol.
 - a. Subjects that score ≤ 23/30 in the Mini Mental State Examination.
5. Patients engaged in an exercise rehabilitation program.
6. Patients schedule to undergo a revascularization procedure during the study.
7. History of angioedema related to use of angiotensin convertase enzyme inhibitor (ACEInh) or angiotensin receptor blocker (ARB).
8. Current use of ACEInh or ARB
9. Concomitant use with aliskiren (renin inhibitors) in patients with diabetes.
10. Renal artery stenosis of more than 60% occlusion in any of the renal arteries by duplex ultrasound.
11. Patients on therapy with lithium compounds.
12. Women who are pregnant or nursing. Women who are not postmenopausal (≥ 12 months of non-therapy- induced amenorrhea) or surgically sterile are defined as being of child-bearing potential, must have a negative result from a urine pregnancy test at Visits 1 and 2. Women with the potential to become pregnant who are not willing to use an acceptable form of birth control, defined as abstinence or use of an intrauterine device (IUD), oral contraceptive, barrier and spermicide, or hormonal implant throughout the study period.
13. Patients with implantable cardiac defibrillators
14. Patients with hyperkalemia (K⁺ > 5.2 mEq/L) and patients with conditions that are the most frequent cause of hyperkalemia, such as CKD and ESRD
15. Patients on potassium sparing diuretics

4.3 Recruitment

Recruitment will be performed with the help of the Clinical and Translational Science Institute (CTSI)

of the University of Minnesota recruiting services and by advertisement in clinics and other institutions with a predominantly elderly population. Patients with PAD who have completed a cardiac rehab programs will receive previously IRB approved letters inviting them to participate in our study. In addition, from the Institute of Health and Informatics, a list of patients with PAD, containing information regarding the date of their upcoming appointment, will be made available to the PI at the secure data shelter. The PI will confirm if the patient meets the inclusion and none of the exclusion criteria on Epic and will send an email to the provider through Epic, requesting that the patient be informed about this clinical trial. If the patient is interested, they will contact the PI to request more information. Our research group has ample experience in recruiting patients with PAD, in maintaining high adherence rate and successfully completing clinical trials^{38,59}. Although PAD is more frequent in African Americans males, we will make an effort to recruit across all racial and ethnic groups and from both genders.

4.4 Early Withdrawal of Subjects

Any subject may discontinue participation in the study for any reason at any time. Subjects who elect to withdraw may resume other treatments as determined appropriate by their physician. Reasons and circumstances surrounding withdrawal will be documented in the study records.

When a pregnancy has been confirmed in a subject during maternal exposure to treatment, the study drug will be discontinued immediately and the subject will be referred to her primary physician. In the event that any subject discontinues study drug and, subsequently, withdraws from the study before completion, regardless of reason, reasonable efforts will be made to have the subject return for an early termination visit and have the end of treatment procedures completed. If a subject is unable to return to the clinic for an early termination visit, attempts will be made to contact the subject by phone to assess AEs. Subjects will be asked to return to the clinic for further assessments if the PI deems it appropriate.

